## 7.7. **Unscheduled Visit**

An unscheduled visit may be performed at any time at the discretion of Investigator in order to further evaluate a subject. The specific assessments to be performed at these visits would be determined by the Investigator according to nature of the subject specific follow-up required, however at a minimum the assessments would include the following:

- Vital signs (temperature, heart rate, respiration rate and blood pressure)
- Symptom-directed physical examination
- Review concomitant medications
- Review AEs
- Laboratory analyses (additional details are provided in the Laboratory Manual):

- Safety labs: chemistry, hematology, coagulation, urinalysis, urine drug test, urine pregnancy test for females of child-bearing potential only (see [Appendix 2](#))
- Virology: HBV DNA, HBV pgRNA, HBsAg, HBeAg, HBcrAg, sample for HBV sequencing, and HBV nucleic acids (see [Appendix 2](#))
- PK samples: samples for ABI-H0731 or PBO and NrtI. See [Section 7.10](#) for additional information on PK sampling.

Assessments performed should be documented in the subject's source documentation. Clinical laboratory assessments should be conducted through the central laboratory.

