### **9.4. Management of On-treatment and Post-treatment ALT Elevations**

All subjects participating in the study will be closely monitored for ALT elevations and/or signs of potential decline in hepatic function. Subjects experiencing ALT elevations  $\geq 2 \times$  Baseline or on-treatment nadir and  $> 2 \times$  ULN during study treatment or during post-treatment follow-up should be closely monitored with regular unscheduled visits every 1 to 2 weeks at the discretion of the Investigator. For these subjects, at each timepoint, an Unscheduled Visit should be conducted with completion of assessments as described in [Section 7.7](#). Additionally, the following guidance is provided for management of subjects with ALT elevations:

- All subjects with an ALT elevation on treatment, defined as ALT  $> 2 \times$  Baseline or on-treatment nadir and  $\geq 10 \times$  ULN, should have the ALT findings confirmed within 3 days of receipt of the original results. To confirm the ALT finding, the subject should return to the clinic for an Unscheduled Visit and undergo all assessments as noted in [Section 7.7](#) (Unscheduled Visit).
- If the ALT elevation is confirmed, then an additional Unscheduled Visit will be performed to further evaluate the subject. At this visit, the following laboratory tests will be performed: ALT, AST, total bilirubin (if total bilirubin is elevated, reflex to Direct Bilirubin), serum albumin, HBV DNA, and quantitative HBV serologies (HBeAg [reflex qualitative HBeAg if quantitative HBeAg is negative] and HBsAg [reflex qualitative HBsAg if quantitative HBsAg is negative]), HAV IgM, HCV RNA, HDV RNA, and HEV IgM.
  - If an intercurrent illness is determined to be causal, subjects with an ALT elevation without declining hepatic function and without contraindications may continue

treatment and the intercurrent illness should be treated as deemed medically appropriate by the Investigator.

- Subjects with an ALT elevation without declining hepatic function and without contraindications may continue treatment with study drug under close observation.

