- If ALT is rising at the confirmatory visit, subjects should return for an **Unscheduled Visit** every 2 to 5 days until the ALT elevation has stabilized. At these visits the following laboratory tests will be performed: ALT, AST, total bilirubin (if total bilirubin is elevated, reflex to Direct Bilirubin), serum albumin, INR, HBV DNA, and quantitative HBV serologies (HBeAg [reflex qualitative HBeAg if quantitative HBeAg is negative] and HBsAg [reflex qualitative HBsAg if quantitative HBsAg is negative]). Subjects whose ALT has stabilized should continue to be monitored weekly (or more frequently, as deemed necessary by the treating physician) until ALT values return to normal or Baseline levels.
  - Subjects with an ALT elevation without declining hepatic function and without contraindications should discontinue study drug if the ALT remains persistently elevated for >4 weeks
- Subjects with confirmed ALT elevation with evidence of declining hepatic function should be discontinued from study treatment. This is defined as:
  - ALT elevation  $\geq 2 \times$  Baseline or nadir and  $> 2 \times$  ULN AND
    - Direct bilirubin increase to  $\geq 2 \times$  Baseline and  $\geq 2 \times$  ULN OR
    - Albumin decline  $\geq 0.5$  g/dL OR INR  $> 2 \times$  Baseline OR
    - Symptoms of liver inflammation (eg, fatigue, weakness, lack of appetite, nausea, vomiting, jaundice, or discolored feces)
- Subjects with evidence of declining hepatic function should return for an **Unscheduled Visit** every 2 to 5 days until the relevant laboratory values stabilize. Subjects whose hepatic function has stabilized should continue to be monitored weekly (or more frequently as deemed necessary by the Investigator) until the relevant laboratory values return to normal or Baseline.
- **Post-treatment ALT Elevation**

Following cessation of study drug treatment under this protocol all subjects will be closely followed for ALT elevations and/or signs of potential decline in hepatic function. This applies to all subjects whether they prematurely discontinue study drug or complete the study per protocol. Any subject with a post-treatment ALT elevation without evidence of declining hepatic function or a post-treatment ALT elevation with evidence of declining hepatic function as defined above, will be evaluated as noted above.

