-  Subjects who discontinue treatment before Week 48 should immediately undergo the assessments listed for the Premature Termination visit and then continue the scheduled follow-up assessments.
-  Any subjects with alanine aminotransferase (ALT) elevation (defined as  $ALT \geq 2 \times$  Baseline and  $\geq 10 \times$  ULN) should return to the clinic for an Unscheduled Visit to confirm the findings within 3 days of receipt of the original results. At the Unscheduled Visit, subjects should undergo the assessments described in [Section 7.7](#). If the ALT elevation is confirmed, the subject will return for an additional Unscheduled Visit at which the following tests: HBV DNA, HBV serologies (quantitative HBeAg [reflex qualitative HBeAg if quantitative HBeAg is negative] and HBsAg [reflex qualitative HBsAg if quantitative HBsAg is negative]), HAV IgM, HCV RNA, HDV RNA, and HEV IgM, will be performed. If the ALT is rising, the subject will return for additional Unscheduled Visits every 2-5 days until the ALT has stabilized. At these visits the following tests will be performed: HBV DNA, HBV serologies (quantitative HBeAg [reflex qualitative HBeAg if quantitative HBeAg is negative] and HBsAg [reflex qualitative HBsAg if quantitative HBsAg is negative]).
-  In addition to the study specific Informed Consent Form, a separate consent is required for the subject to provide an optional pharmacogenomic sampling.
-  Liver staging is to be performed to determine lack of cirrhosis or advanced liver disease as required by inclusion criteria and should be performed in a fasted state by FibroScan or other Sponsor-approved hepatic imaging method within 3 months of Screening.
-  Height is measured at the Screening visit only.
-  For the complete physical examination, assessment of the breasts and genitalia are not required unless indicated.
-  Complete physical exam and weight measurement are performed only at Weeks 48 and 96 visits, and at 24 Week post-treatment visit (if applicable).
-  A Symptom-directed physical exam is performed only at the visits when a complete physical exam is not performed.
-  During the study, any clinically significant ECG result or change from Baseline (Day 1) should be confirmed, and if confirmed, should be recorded as an AE. 12-lead ECG to be also performed at Weeks 24, 36, 48, and 96.

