**Table 8: Clinical Laboratory Tests**

Panel	Tests
Clinical chemistry	Blood glucose levels, serum or plasma electrolytes (sodium, potassium, chloride, bicarbonate), calcium, blood urea nitrogen, serum creatinine, creatine kinase, GFR, uric acid, total and direct bilirubin a , ALT, AST, GGT, alkaline phosphatase, LDH, amylase, triglycerides, total cholesterol, inorganic phosphate or total phosphate, total protein, albumin, lipase, and total serum or plasma globulins
In case of elevated ALT	ALT, AST, total bilirubin, serum albumin, and INR
Hematology	Complete blood counts: hemoglobin, hematocrit, RBC indices (MCV, MCHC), reticulocyte counts, leukocyte counts (total and differential), and platelet counts
Coagulation	Prothrombin time/INR and aPTT
Urinalysis	pH, specific gravity, protein, glucose, ketones, and occult blood
Other	AFP, HbA1c, and FSH
Pregnancy tests	For females of child-bearing potential only; a serum or plasma pregnancy test must be performed at Screening, and both serum/plasma and urine are required at Day 1; a serum, plasma, or urine pregnancy test must be performed at all subsequent visits. A positive result disqualifies the subject for study treatment
Urine drug screening	Amphetamine/methamphetamine, barbiturates, benzodiazepines, cocaine metabolite, ecstasy, ethanol, opiates, phencyclidine, and propoxyphene.
Antibodies	HCV, HDV, HAV IgM, HEV IgM, and HIV

Abbreviations: AFP=alpha fetoprotein; ALT=alanine aminotransferase; aPTT=activated partial thromboplastin time; AST=aspartate aminotransferase; FSH=follicle-stimulating hormone; GGT=gamma-glutamyl transpeptidase; GFR=glomerular filtration rate; HAV=hepatitis A virus; HbA1c=hemoglobin A1c; HCV=hepatitis C virus; HDV=hepatitis D virus; HEV=hepatitis E virus; HIV=human immunodeficiency virus; IgM=immunoglobulin M; INR=International Normalized Ratio; LDH=lactate dehydrogenase; MCHC=mean corpuscular hemoglobin concentration; MCV=mean corpuscular volume; RBC=red blood cell; ULN=upper limit of normal.

a Perform fractionated bilirubin, if total bilirubin >ULN.

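### Section 9.4 stops study drug on direct bilirubin, but both of its test lists and Table 8 footnote a order direct bilirubin only when total bilirubin is elevated

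*Combined protocol and SAP*

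**What the plan says.** **Stopping rule.** Section 9.4 requires discontinuation for a confirmed ALT elevation (at least 2× Baseline or nadir and above 2× ULN) with declining hepatic function. Any one of four legs shows decline: direct bilirubin, albumin, INR or symptoms. The first begins "Direct bilirubin increase to" and sets the level at no less than twice Baseline and no less than twice the ULN. It does not mention total bilirubin.

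**Tests ordered in Section 9.4.** For the additional visit after confirmation, the list includes "total bilirubin (if total bilirubin is elevated, reflex to Direct Bilirubin), serum albumin, HBV DNA". For the visits every 2 to 5 days while ALT is rising, it includes "total bilirubin (if total bilirubin is elevated, reflex to Direct Bilirubin), serum albumin, INR, HBV DNA".

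**Unscheduled Visit minimum.** For the closer-monitoring visits every 1 to 2 weeks, Section 9.4 says "an Unscheduled Visit should be conducted with completion of assessments as described in" Section 7.7, and it sends the confirmatory visit there as well. The Section 7.7 minimum has "Safety labs: chemistry, hematology, coagulation, urinalysis, urine drug test". Appendix 1 marks chemistry and coagulation in the Unscheduled Visit column.

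**Table 8.** The chemistry row names "uric acid, total and direct bilirubin", but footnote a on that entry calls for fractionation when total exceeds the ULN. The row for elevated ALT reads "ALT, AST, total bilirubin, serum albumin, and INR", without direct bilirubin.

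**Entry.** Exclusion 13 (Section 5.3) lists direct bilirubin above 1.2× ULN as an item separate from total bilirubin.

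**The concern.** A stopping criterion works only if the quantity it uses is measured whenever the criterion has to be judged. Here the criterion is stated in direct bilirubin alone, while the ordering instructions make direct bilirubin depend on a different result. Direct bilirubin is one of the four legs that separate continuing under observation from stopping drug. If the laboratory follows the reflex wording, a subject with raised direct and normal total bilirubin can meet that leg without anyone seeing it. The same condition affects the Baseline value on which the leg depends and the separate entry limit in Exclusion 13.

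**Working it through.** The plan states no figure to reproduce. The check is a comparison of provisions, followed by one piece of arithmetic on assumed limits.

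**1. What the leg needs.** Three quantities: direct bilirubin at the visit, direct bilirubin at Baseline, and the direct ULN. Total bilirubin is not an input.

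**2. What is ordered.** The two Section 9.4 lists need not be the whole order set. The visits they describe are Unscheduled Visits, so the Section 7.7 minimum applies. Appendix 1 footnote 3 supports this: where it says "the subject will return for an additional Unscheduled Visit at which the following tests", it goes on to name only virology and serology, which fits tests added to a standing panel. So at Screening, on Day 1 and at every ALT-triggered visit, the question comes down to the chemistry entry in Table 8 and its footnote a.

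**3. Two readings of that entry.**
- *Routine:* direct is always run. This fits the panel row, Exclusion 13 and the Baseline term in the stopping leg. It leaves footnote a and both Section 9.4 parentheses with nothing to do.
- *Reflex:* direct is run only when total exceeds its ULN. This fits footnote a and both Section 9.4 lists. It leaves Exclusion 13 and the stopping leg without data when total is normal.

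**4. Consequence of the reflex reading for the stopping leg.**

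| Total on Day 1 | Total at the ALT-triggered visit | Can the leg be judged? |
|---|---|---|
| Normal | Normal | No: direct is not run |
| Elevated | Normal | No: direct is not run |
| Normal | Elevated | Only in part: 2× ULN can be checked, but there is no Day 1 direct value for 2× Baseline |
| Elevated | Elevated | Yes |

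Exclusion 13 bars total above 1.2× ULN except in known Gilbert's syndrome. The last row is therefore limited to Day 1 totals between 1.0× and 1.2× ULN, plus subjects with Gilbert's syndrome.

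**5. Can direct reach its threshold while total is normal?** Direct is part of total, so this is possible only if

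2 × direct ULN ≤ total ULN, that is, direct ULN ≤ ½ × total ULN.

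The documents give no bilirubin ULNs. *Assumed range:* direct ULN 0.2 to 0.6 mg/dL and total ULN 1.0 to 1.3 mg/dL, each in steps of 0.1 (5 × 4 = 20 combinations).

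| Direct ULN | 2 × direct ULN | Possible with normal total? | Direct share needed with total at its ULN |
|---|---|---|---|
| 0.2 to 0.4 | 0.40 to 0.80 | Yes, at every total ULN | 0.40/1.3 = 31% to 0.80/1.0 = 80% |
| 0.5 | 1.00 | Yes, at every total ULN | 1.00/1.3 = 77% to 1.00/1.0 = 100% |
| 0.6 | 1.20 | Only at total ULN 1.2 or 1.3 | 1.20/1.3 = 92% to 1.20/1.2 = 100% |

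The condition holds in 12 + 4 + 2 = 18 of the 20 combinations. A larger direct share is needed if total is below its ULN.

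**6. The Exclusion 13 limit.** 1.2 × direct ULN runs from 1.2 × 0.2 = 0.24 to 1.2 × 0.6 = 0.72 mg/dL. That is below the lowest assumed total ULN of 1.0, so the limit can be exceeded with normal total throughout the range.

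**The case against.** The strongest reply is that direct bilirubin is measured anyway. Chemistry is part of the minimum at every Unscheduled Visit, the panel names direct bilirubin, and Exclusion 13 cannot be cleared without a direct result. Section 7.1 allows no waivers, and a rule written as a multiple of Baseline presupposes a Baseline value. Test-order details are also left to the Laboratory Manual, which is not among the documents. This is a plausible reading, and it rules out a stronger inference that a reader might draw, namely that direct bilirubin is never measured when total is normal. It does not settle the matter, because footnote a sits on the very panel entry it relies on and both Section 9.4 lists repeat the condition.

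The backstops also stand. An albumin fall of 0.5 g/dL or more, INR above 2× Baseline, or symptoms as mild as fatigue or nausea is each enough with the ALT condition. ALT that stays elevated for more than 4 weeks stops drug as well.

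Three further inferences are tempting and not supported:
- *That ineligible subjects would be enrolled.* This needs a site to pass a written criterion with no result in hand. The documents show only that the limit could not be checked.
- *That 18 of 20 indicates how often the problem arises.* The combinations are assumed reference limits, not patients.
- *That every case with total above its ULN is captured.* On the reflex reading this fails when Day 1 total was normal, because the Baseline comparison cannot be made.

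The direct-bilirubin grade in Appendix 3 adds little. It requires signs and symptoms of hepatotoxicity or life-threatening consequences, and symptoms of liver inflammation are already a stopping leg.

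**Conclusion.** The protocol gives conflicting instructions. One leg of the Section 9.4 stopping rule depends on direct bilirubin alone, while both test lists and Table 8 footnote a make that measurement conditional on elevated total. If the condition is followed, the leg is not assessed when total is normal, it can be only partly assessed when total was normal on Day 1 and rises later, and the Exclusion 13 direct limit cannot be checked when total is normal.

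The effect is small. The gap is arithmetically possible whenever the direct ULN is at most half the total ULN; that rests on assumed limits and shows possibility, not frequency, which is unknown. The other legs and the 4-week ALT rule cover part of it. The SAP reports early termination with 2 subjects randomized and plans listings only, so no analysis depends on this point. It is a cheap improvement, and it does not show that any subject was harmed or wrongly enrolled.

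**What to change.** Make direct bilirubin unconditional at Screening, Day 1 and all ALT-triggered visits:

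- Amend Table 8 footnote a to say so.
- Delete the condition on elevated total from both Section 9.4 test lists.
- Add direct bilirubin to the Table 8 row for elevated ALT.
- Align the central-laboratory order.

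No clinical threshold changes. The cost is one low-cost assay on serum already drawn at existing visits, plus the wording edits. There may be an occasional stop with normal total, but the rule as written already requires that stop. As the study has ended, what remains useful is to check whether direct bilirubin was reported for the 2 randomized subjects and to correct the text before it is reused.

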## 10. STATISTICAL CONSIDERATIONS

This section provides the key details of the statistical analyses for a final analysis to be performed using data captured according to this protocol. No interim analysis is planned for this study. A complete SAP describing all planned analyses will be finalized prior to database lock.

### 10.1. Determination of Sample Size

Approximately, 40 subjects with CHB will be enrolled in the study. Subjects will be randomized to receive either 300 mg ABI-H0731 or matching PBO in a 1:1 ratio in addition to standard of care NrtI. Since this is a proof-of-concept study, sample size is similar to that previously utilized for this type of study and is not based upon statistical considerations.

### 10.2. Analysis Populations

The following populations will be considered for analysis of various endpoints:

*Randomized Set:* It includes all randomized subjects who satisfied the inclusion and exclusion criteria described in this protocol.

*Full Analysis Set:* It is the main analysis population for the efficacy analysis. It includes all randomized subjects, classified according to the treatment arm into which they were randomized regardless of the actual treatment received, who used any amount of study drug and have at least 1 post-baseline efficacy assessment.

*Safety Set:* It includes all subjects, classified according to the actual treatment received regardless of random assignment, who used any amount of study drug and have at least 1 post-baseline safety evaluation. This is the main analysis population for all safety analyses.

*PK-Evaluable Set:* It consists of all subjects, classified according to the actual treatment received regardless of random assignment, who receive at least 1 dose of study drug. A Baseline and at least 1 PK blood sample following a dose of study treatment is required for inclusion in this analysis. This is the main analysis population for all PK analyses.

Based on the actual deviations, the criteria for exclusion of subjects from the different data sets will be specified and updated, if necessary, prior to database lock.

### 10.3. Planned Analyses

As a general strategy, continuous efficacy and safety endpoints will be summarized using the five-number summary (mean, standard deviation, median, minimum, and maximum). Frequency distributions (counts and percentages) will be used to summarize categorical endpoints.

Analyses by treatment group will be presented as follows:

- Efficacy analyses: according to the treatment to which subjects were randomized
- Safety and PK analyses: according to the treatment received

The primary analysis of the study will be performed when all subjects complete Week 48 evaluations.

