**Study Design:** This is a Phase 2a, multi-center, randomized, single-blind, PBO-controlled study, evaluating the safety, antiviral activity, and pharmacokinetics (PK) of ABI-H0731 administered in addition to standard of care NrtI in subjects with CHB who have not achieved adequate virologic suppression of HBV DNA <LLOQ on NrtI alone. For this

study, HBV DNA is analyzed by COBAS® TaqMan Version 2.0 at the central laboratory (lower limit of quantification [LLOQ]=20 IU/mL).

Approximately 40 eligible subjects will be randomized in a 1:1 ratio to the treatment groups described below.

Abbreviations: NrtI=nucleos(t)ide reverse transcriptase inhibitor; PBO=placebo; QD=once daily; Wk=week.

Treatment with ABI-H0731 or PBO and NrtI will be administered orally, once daily

- Group 1 will receive ABI-H0731+NrtI for 96 weeks
- Group 2 will receive PBO+NrtI for 48 weeks, and then ABI-H0731+NrtI until Week 96

All subjects will continue to receive NrtI alone from Week 96 through Week 120 (during the 24-week follow-up period).

The study will enroll up to 75% subjects on entecavir (ETV). Treatment assignments will be stratified by the concurrent NrtI administered (ie, ETV) versus tenofovir (alafenamide versus [TAF] or disoproxil fumarate [TDF]) and HBV DNA (HBV DNA  $\geq$ 500 IU/mL versus <500 IU/mL) during the Screening visits.

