## 4. STUDY PLAN

### 4.1. Study Design

This is a Phase 2a, multi-center, randomized, single-blind, PBO-controlled study, evaluating the safety, antiviral activity, and PK of ABI-H0731 administered in addition to standard of care NrtI in subjects with CHB who have not achieved adequate virologic suppression of HBV DNA <LLOQ on NrtI alone. For this study, HBV DNA is analyzed by COBAS TaqMan® Version 2.0 at the central laboratory (LLOQ=20 IU/mL).

The study will be conducted at approximately 10 study centers worldwide. Approximately 40 eligible subjects will be randomized in a 1:1 ratio to the treatment groups shown in the study overview presented in [Figure 4](#).

Study investigational drugs, ie, 300 mg (3×100 mg tablets) ABI-H0731 or matching PBO (3 tablets) and subjects' background NrtI therapy will be administered orally, once daily (QD). Group 1 will receive ABI-H0731+NrtI for 96 weeks, Group 2 will receive PBO+NrtI for 48 weeks followed by ABI-H0731+NrtI for 48 weeks until Week 96. All subjects will continue to receive NrtI alone during the 24-week follow-up period from Week 96 through Week 120.

Treatment assignments will be stratified by the concurrent NrtI administered (ie, ETV) versus tenofovir (alafenamide versus [TAF] or disoproxil fumarate [TDF]) and HBV DNA (HBV DNA ≥500 IU/mL versus <500 IU/mL) during the Screening visits. The study will enroll up to 75% subjects on ETV. Safety, antiviral activity, and PK will be assessed during treatment and the 24-week follow-up period.

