#### **10.3.7.1. TEAEs**

Treatment-emergent adverse events reported during the study will be coded using the Medical Dictionary for Regulatory Activities (MedDRA) dictionary. Incidence of TEAEs will be summarized by treatment group and the following:

- Preferred term
- System organ class and preferred term
- System organ class, preferred term, and severity

These summaries will be presented for the following subsets:

- All adverse events
- Serious adverse events
- Drug-related adverse events

For tables reporting adverse events by severity, if a subject has multiple occurrences of an adverse event with the same organ class and preferred term, the most severe event will be presented.

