### **3. GENERAL CONSIDERATIONS FOR DATA ANALYSES**

Statistical analysis will not be performed for this study. Only listings will be provided.

By-subject listings will be presented for all subjects in the All Randomized Analysis Set and sorted by subject ID number, visit date, and time (if applicable) in chronological order within the subject. The treatment group to which subjects were randomized will be used in the listings.

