#### **7.1.5. Treatment-Emergent Adverse Events**

##### **7.1.5.1. Definition of Treatment-Emergent Adverse Events**

Treatment-emergent adverse events (TEAEs) are defined as any AEs with an onset date on or after the study drug start date and no later than 28 days after permanent discontinuation of study drug.

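### Does the safety analysis by treatment received need a split at the Week 48 crossover?

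*Combined protocol and SAP*

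**What the plan says.** The design in protocol Section 4.1 builds in a switch: "Group 2 will receive PBO+NrtI for 48 weeks followed by ABI-H0731+NrtI for 48 weeks until Week 96". The Synopsis gives the other arm: "Group 1 will receive ABI-H0731+NrtI for 96 weeks".

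For safety, Section 10.3 states "Safety and PK analyses: according to the treatment received". Section 10.2 defines the Safety Set in the same terms: "It includes all subjects, classified according to the actual treatment received regardless of random assignment". Section 10.3.7.1 adds "Incidence of TEAEs will be summarized by treatment group and the following" and then lists the coding levels, with no split by period. The primary safety endpoint in Section 3.2.1 is a proportion of subjects with no timepoint, whereas the efficacy endpoint beside it is fixed at Week 48. Section 10.3 also says that the primary analysis takes place once all subjects have completed Week 48. Sections 10.3.7.2 and 10.3.7.3 summarize laboratory values by visit and vital signs by time point.

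The SAP was written after early termination. Section 1 reports 2 subjects randomized. Section 3 says that no statistical analysis will be done and only listings produced, and adds: "The treatment group to which subjects were randomized will be used in the listings". Section 7.1.5.1 ends the treatment-emergent window "no later than 28 days after permanent discontinuation of study drug". Section 4.2 provides an exposure listing with planned group, actual drug received, and dose start and end dates.

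**The concern.** Classifying by actual treatment normally deals with subjects who were given the wrong arm's drug. Here the crossover is planned, so the rule does not place a Group 2 subject who passes Week 48 in a single group. There are two readings, and each distorts a whole-study incidence table.

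- **By drug taken.** Group 2 contributes to both columns. The active column then holds up to 96 weeks per subject and the placebo column 48, so an inert drug would appear to cause more events.
- **By randomized sequence.** Group 2 events that begin on ABI-H0731 fall under the placebo-first arm, and a real drug effect is diluted.

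Section 10.3.7 defines baseline as the assessment before first dose. Group 2 changes after the switch would therefore be measured from a value taken 48 weeks before that subject began ABI-H0731. The SAP's treatment-emergent window does not restart at the switch, and its use of the randomized group in the listings departs from the protocol's treatment-received rule. Safety is a primary objective, so in a completed 40-subject trial the main safety table would have lacked a defined comparison.

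**Working it through.** **Plan's own figure.** The protocol gives 20 + 20 = 40 subjects (Sections 6.1.1 and 10.1), stated not to rest on statistical considerations. There is no power calculation or event rate to reproduce.

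**Exposure, assuming all subjects complete.**

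- Active, full study: 20 × 96 + 20 × 48 = 2,880 subject-weeks.
- Placebo: 20 × 48 = 960 subject-weeks. The ratio is 3:1.
- With each subject's data cut at Week 48: 20 × 48 = 960 in each arm, ratio 1:1.
- At the primary analysis with no per-subject cut, earlier enrollees carry extra weeks. Enrollment duration is not given. If enrollment is uniform over S weeks, the mean excess is S/2, and active exposure is 20 × (48 + S/2) + 20 × S/2. For S = 12, 24 and 48 this gives 1,200, 1,440 and 1,920 subject-weeks against 960.

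**Common events with no drug effect.** Assume a constant, equal hazard. If q is the 24-week rate, incidence by week w is 1 − (1 − q)^(w/24). Study 211 gives q = 44/92 in Table 2 of the protocol; the text of Section 2.2.3.2.1 says 42/92.

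| q | 48 weeks | 96 weeks | Group 1 minus placebo | Pooled active minus placebo |
|---|---|---|---|---|
| 44/92 | 72.8% | 92.6% | 19.8 points | 9.9 points |
| 42/92 | 70.5% | 91.3% | 20.8 points | 10.4 points |

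Pooled active is the mean of the 48- and 96-week figures, because 20 subjects have each duration. Over assumed q of 10% to 70%, the Group 1 gap runs from 8 to 25 points and the pooled gap from 4 to 13.

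**Rare events.** Take q = 2/92, the Grade 3 or 4 row of Table 2.

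- No drug effect: 1 − (90/92)^2 = 4.3% at 48 weeks and 1 − (90/92)^4 = 8.4% at 96 weeks, a ratio of 1.96. In 20 subjects that is about 0.9 against 1.7 people.
- Hazard doubled on ABI-H0731, whole study, grouped by sequence: Group 1 is 1 − (90/92)^8 = 16.1% and Group 2 is 1 − (90/92)^6 = 12.4%. The ratio is about 1.3, against 1.96 at Week 48.

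**What the operative plan computes.** The SAP calls for no proportion, difference or group summary, and its listings cover 2 subjects. None of the quantities above will be calculated, so the distortion in the reported results is nil.

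**The case for a change.** The strongest case for a change is that the protocol was written for 40 subjects and left a primary endpoint without a defined comparison, whatever happened later. Holding the primary analysis at Week 48 does not cure this. It is triggered by the last subject, no per-subject cut is stated, and the cumulative final analysis would still come. The SAP keeps a trace of the problem: its listings use the randomized group, and Section 7.1.6 does not require the adverse-event listing to show the drug taken at onset.

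As criticism of the protocol text, much of this stands. One sentence limiting the between-group safety comparison to the period before the switch, with later data reported separately from a Week 48 baseline for Group 2, would have been better.

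Some of it is weaker than it looks. The text is ambiguous and does not commit to counting Group 2 twice; the protocol's treatment groups can fairly be read as the two randomized sequences. By-visit laboratory and time-point vital-sign summaries already separate values before and after the switch. That leaves the cumulative adverse-event, discontinuation and abnormal-laboratory proportions, and the shift tables, exposed. Section 10 also left the full analysis detail to the SAP, where a Week 48 cut would be the ordinary choice.

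An added drug-at-onset column would only repeat what can be read by setting event dates beside the dose dates in the SAP Section 4.2 listing.

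**Conclusion.** The omission is genuine, but correcting it gains nothing. In a completed trial reported on whole-study data it could have produced a spurious gap of about 20 points in common adverse events, or shrunk a true doubling of a rare event to a ratio of about 1.3. Those sizes depend on a constant hazard, on rates borrowed from an open-label extension study, on full completion and on no cut at Week 48. They illustrate the direction of the problem and do not predict its size.

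Under the SAP that governs the report, 2 subjects are listed individually and no group incidence is produced. Rewording protocol Section 10.3.7 would alter no table and no conclusion. The documents do not say whether either subject reached Week 48, so the switch may not appear in the data at all. If it does, the listed drug and dose dates let a reader place each event. This assumes that event onset dates appear in the adverse-event listing, which is reasonable because the treatment-emergent definition needs them. The point is a low-severity note on wording.
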